Aim 1a. Test the efficacy (3-month situation appropriate testing or vaccination) of a network diffusion motivational intervention versus an educational intervention among: 1) primary study participants (primary outcome); and 2) secondary study subjects connected to primary participants (secondary outcome) using a randomized controlled trial design.

Aim 1b. Examine differential intervention effects by individual and network-level characteristics that may increase situation appropriate testing and/or vaccination uptake, such as age, prior COVID-19 infection, mental health status, historical trauma, early adopter status, COVID-19 prevention behaviors, government mistrust, network testing/vaccination and prior infection, and network density. We will also explore hypothesized individual and network level mechanisms through which the intervention works (e.g., increased knowledge, self-efficacy, trust).

STUDY SITES

The sample (n=800 primary participants and $n\sim 3,200$ secondary subjects (~2-4 network members per participant) will be spread across four jurisdictions: Baton Rouge, LA; Little Rock, AR; Chicago, IL and Indianapolis, IN.

Table 1: Breakdown of study sites

Study Sites	Site Lead	Stakeholders	IRB of Record	Sample Size(n)
Chicago, IL University of Chicago	[name]	Chicago Dept. of Public Health	University of Chicago IRB	150
Pulaski Cnty., AR University of Arkansas for Medical Sciences	[name],	Arkansas Dept of Health and Central Arkansas Housing Corporation (CAHC)	University of Chicago IRB	250
Baton Rouge, LA Capitol Area Reentry Program (CARP)	[name]	Aspire Health Care	University of Chicago IRB	250
Indianapolis, IN Indiana University	[name], [name]	Inner Beauty, New B.O.Y., VOICES	Indiana University IRB	150
Northwestern University Evanston, IL	[name]	NA	University of Chicago IRB	NA
NORC	[name]	All study sites. NORC will assist with site management and training, as well as study design and data analysis.	University of Chicago IRB	NA

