We hypothesize that primary study participants randomized to receive the Motivational intervention condition (tailored motivational messaging plus network diffusion in a group setting with 1-month booster communication) will be more likely to get tested and/or vaccinated within 3 months of the intervention as compared to COVID-19 Education condition alone (attention control). We also hypothesize that Motivational intervention will result in more secondary study subjects (network members of primary participants) will receive testing and/or vaccination within 3 months. Finally, we anticipate that there may be differential intervention effects across participant characteristics across study sites, by mental health, exposure to law enforcement, prior COVID-19 infection, testing frequency, age and network composition, and will explore these sub-group differences in the context of any power limitations.

RECRUITMENT OF STUDY PARTICIPANTS

We will enroll 800 study participants ages ≥ 18 years of age across all four sites. Study participants will be recruited by local research assistants (RAs) embedded within community settings that provide a number of in-person and remote social and care services, including community COVID-19 testing and vaccination. We will utilize several strategies that we have utilized previously.^{22,54-58}

Recruitment activities may include:

- In-person recruitment may be conducted at the study center (Table 1), during regular drop-in and community-based services, and events occurring at the study center and its outreach programs. This may include providing a study flyer or contact card so that a client can contact the study team directly about participation. A sign-up sheet may also be provided, where interested clients can provide their contact information if they wish to be contacted by the study team about the study.
- Flyers posted at study centers
- Social media postings
- Contacting individuals from previous studies who have indicated interest in being contacted for future work or from existing community programs.

All participants will be asked to sign a release of information so that the study team receives COVID-19 testing/vaccination results as part of existing COVID-19 testing and vaccine registries in the four locations.

Inclusion and Exclusion Criteria.

Inclusion Criteria:

- (1) ≥ 18 years of age
- (2) spend majority of their time in the metropolitan area or county where recruited
- (3) primary communication in English

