- 5) Visually displaying any piece of mail listing the subject's name and address
- 6) Asking the subject to verbally state their name

Baseline Surveys:

The Locator Form and Baseline Assessment is completed at the time of enrollment. These are completed electronically and may be done in person using a study laptop or remotely via telephone or video call.

Randomization. Study participants will be randomized to receive the Education or Motivational intervention at a 1:1 ratio. Randomization will be performed at the participant level, meaning that in general, participants within a site will be assigned to different groups. Randomization will be stratified by site as well as by key participant characteristics such as prior infection/vaccination, to ensure balance. Random assignments will be provided via a web-based API, with the touchpads programmed to retrieve an assignment at the appropriate time and deliver message to staff so they can direct the participant to the appropriate room.

C3 Intervention: COVID-19 Testing and Vaccination Network Intervention Condition. Study participants randomized to the Motivational Intervention will receive the intervention using a social network diffusion approach. The Motivational intervention will be based upon a previous workshop divided into four learning and practice modules (Table 2 below).

Table 2. Motivation Intervention**C3 Intervention Components adapted from RADx-UP Phase I and PrEPChicago.**

Strategy	Content	Duration	Intervention Strategy Source(s)
Fact or Myth session with sub-group role-play	COVID-19 prevention Fact or Myth session 1) different types of tests and vaccines; 2) technology, clinical development and effectiveness; 3) vaccine dosing administration and relationship to prior COVID-19 infection; 4) potential side-effects; and 5) how to access it.	45 minutes	PrEPChicago/RADx-UP Phase I
Situation Appropriate COVID-19 Prevention	Knowing the network member's COVID-19 history (ie. prior infection, recent exposure). Discussion of indications for testing (ie. COVID-19 symptoms, known exposure) and vaccination post-infection. Testimonials around misinformation, correction and discussion.	45 minutes	RADx-UP Phase I

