Primary Outcomes. Two primary outcomes will be assessed at the level of the participant: the probability of receiving at least one 1) test and 2) vaccination dose within 3 months of baseline. Outcomes will be ascertained specifically by testing/vaccine registry data held by city and state held vaccine registries (Letters, [name], [name], [name]). Study participants will sign release of information forms, as in RADx-UP Phase I, in order for study staff to obtain 3-month testing/vaccination disposition statuses. Covid testing/vaccination status may also be provided by subject showing a copy of their covid testing result and/or vaccination information. This may be provided in person, shown during a video call, emailed or texted as a picture. Finally, study staff will reach out to all study participants (N=800) at 3 months following baseline to collect information on testing and vaccination uptake among study participants and barriers and facilitators for both network members and study participants. During

this assessment, information on situation appropriate testing will be collected to better understand the circumstances and context of testing. At the time of this writing, situation appropriate testing includes testing if symptomatic, if exposed to someone with COVID-19 infection and if entering a congregate living setting. Only participants reporting symptoms, exposure, and/or congregate housing will be included in the primary testing outcome analysis; post-hoc analysis will include all participants tested irrespective of the situation/context.

Secondary Outcome. Two secondary outcomes will be assessed at the level of the secondary subjects (network member connected to primary participant): the probability of receiving at least one 1) test and 2) vaccination dose within 3 months of baseline. Network member information, including identifying information will be collected during the baseline assessment through specialized network canvas software (described above). The secondary outcome will be determined based upon self-report from participants during the 30 and 90-day follow-up surveys. Note that this information is collected based asking the study subject whether the social network contact underwent these activities and not from contact with or medical record data collection of the social network member. Analyses for our secondary outcome will account for variability in network size across individuals.

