Primary and Secondary Outcome Analysis. Two sets of analyses will be performed. The first will focus on testing and vaccination among participants and the second will focus on testing and vaccination among the networks of participants. Testing and vaccination will be analyzed as separate outcomes throughout. The primary outcome analysis will compare the probability of testing and the probability of vaccination among participants assigned to Educational vs. Motivational intervention. Secondary analyses will compare the total number of network members tested and vaccinated and the probability of testing/ vaccination among network members of participants assigned to Educational vs. Motivational intervention (Aim 1). All analyses will use generalized linear models with link functions based on the distribution of the outcome (logistic or log binomial for binary outcomes; negative binomial regression for count outcomes) and random effects as appropriate to account for clustering of network members within participants. The initial analysis will include an indicator for intervention assignment as the only independent variable and will not adjust for covariates since the randomization should ensure comparability between the groups on measured and unmeasured confounders, though group characteristics at baseline will be inspected visually for imbalances (Aim 1a). We will then incorporate participant (e.g., mental health, early adopter status) and network level (e.g., network thresholds, density) covariates to improve the precision of the estimates and to identify sociodemographic and network characteristics associated with differences in testing and vaccination yield. In addition, we will explore interactions between intervention group (Education vs. Motivational intervention) and participant characteristics to determine whether the intervention is more effective in certain groups than

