Power Calculations. Statistical power for Aim 1 was computed across a range of plausible effect sizes and outcome prevalence estimates. Power was estimated conservatively, assuming that of the 800 total participants and their network members, 10% would meet the current CDC recommended criteria for testing (recent exposure, symptoms, or congregate housing) and thus the sample size for the primary testing outcome was estimated at N=80 eligible participants. We assumed that 30% would previously have been fully vaccinated or infected with COVID-19 in the past 6 months, resulting in an analytic sample size for vaccination outcomes of N=560 participants and their network members. Power may change depending on the evolution of the pandemic (e.g., changes in infection rates, prevalence of variants, and/or local public health guidance regarding testing and booster vaccine recommendations), and will be higher with broader testing eligibility, higher outcome prevalence, and for analyses treating each network member as a separate observation. For each outcome, we computed minimum detectable effect sizes given estimated rates of testing and vaccination in the control group. We estimated 3-month testing rates among those eligible for testing of 10% in the control group. Based on our ongoing influenza vaccination work, as a starting point for calculations we estimated 3-month vaccination rates among study participants and their network members of approximately 30%. All calculations were conducted in Stata/SE version 15.1 with alpha=0.05, two-sided tests, and a 2:1 ratio of randomization to the intervention vs. control group. For participant testing (primary outcome 1), with a sample size of 80 eligible participants and control group testing prevalence of 10%, we would have 80% power to detect differences of 28 percentage points or more (proportion tested in the intervention group $\geq 38\%$). For participant vaccination (primary outcome 2), with a sample size of 560 and vaccination prevalence of 30% in the control group, we would have 80% power to detect differences of ≥ 12 percentage points (proportion vaccinated in the intervention group $\geq 42\%$). For evaluating interaction effects (Aim 1b), with a sample size of 560 we would have $>80\%$ power to detect an interaction between intervention assignment and an evenly distributed binary covariate (50% in group A and 50% in group B) when vaccination prevalence in the control group is 30% and the intervention increases vaccination to 40% in group A and 69% in group B (e.g., the intervention is more effective in group B). For the participant testing outcome, we will have limited power to detect interaction effects except those of very large magnitude, but will explore differences in testing across

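### Two primary outcomes, each powered at the full two-sided 0.05 under an either-or efficacy aim, have no multiplicity rule for the pair

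*Combined protocol and SAP*

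**What the plan says.** The Primary Outcomes section states: "Two primary outcomes will be assessed at the level of the participant". They are receipt of at least one test and of at least one vaccine dose within 3 months. The outcome analysis section adds: "Testing and vaccination will be analyzed as separate outcomes throughout". There is no composite and no global test.

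Aim 1a joins the two outcomes in one efficacy statement: "Test the efficacy (3-month situation appropriate testing or vaccination) of a network diffusion motivational intervention". The hypothesis in Methods is directional and also joins them: Motivational participants "will be more likely to get tested and/or vaccinated within 3 months of the intervention".

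The only significance level in the document is in Power Calculations: "All calculations were conducted in Stata/SE version 15.1 with alpha=0.05, two-sided tests". It is applied in full to each primary outcome. The outcome analysis section gives no level, split of alpha, ordering of the outcomes or requirement that both succeed. Multiple comparisons are addressed only for the exploratory interaction tests, through Bayesian partial pooling.

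The power section also assumes "a 2:1 ratio of randomization to the intervention vs. control group", whereas the Randomization paragraph says: "Study participants will be randomized to receive the Education or Motivational intervention at a 1:1 ratio". This has no bearing on the error rate, but it changes the cost of any adjustment.

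**The concern.** Under the wording of Aim 1a, a positive result on either outcome can be reported as support for efficacy. The claim then has two chances to succeed, and nothing in the plan limits the combined error. For example, a p-value between 0.025 and 0.05 on one outcome, with nothing on the other, could be presented as meeting the aim. With no decision rule written down, the rule could also be chosen after the results are known. The plan recognises multiplicity for its exploratory interactions but leaves the confirmatory pair without a provision.

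**Working it through.** **Inputs.** From Power Calculations: two-sided alpha 0.05; testing N=80, 10% control against 38% intervention; vaccination N=560, 30% against 42%; 80% power for each; 2:1 allocation. From Randomization: 1:1 allocation. The documents give no correlation between the two test statistics, so a range is shown.

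**1. Reproducing the plan's power (2:1, alpha 0.05).** Normal approximation without continuity correction: power = Φ[(|p2 − p1| − z·s0)/s1]. Here s0 = √{p̄(1−p̄)(1/n1+1/n2)}, s1 = √{p1(1−p1)/n1 + p2(1−p2)/n2}, and p̄ is the allocation-weighted mean proportion.

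- Testing: p̄ = 0.2867, s0 = 0.1073, s1 = 0.0883. Power = Φ[(0.28 − 1.960×0.1073)/0.0883] = 78.5%.
- Vaccination: p̄ = 0.38, s0 = 0.0435, s1 = 0.0422. Power = Φ[(0.12 − 1.960×0.0435)/0.0422] = 79.5%.

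Both agree with the stated 80% to within 2 points. The differences detectable with exactly 80% power are 28.5 and 12.1 points. The stated figures therefore use the full 0.05 for each outcome and 2:1 allocation.

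**2. Error rate if each outcome is tested at two-sided 0.05, both nulls true.**

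- Any false positive, either direction, independent tests: 1 − 0.95² = 9.75%.
- False claim favouring the Motivational arm, independent tests: 1 − 0.975² = 4.94%. One test alone gives 2.5%.

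| Correlation of test statistics | Either direction | Favouring Motivational |
|---|---|---|
| 0 | 9.75% | 4.94% |
| 0.3 | 9.51% | 4.76% |
| 0.5 | 9.07% | 4.54% |
| 0.9 | 7.04% | 3.52% |

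For jointly normal statistics 9.75% is the maximum in either direction. The bounds that need no distributional assumption are 10% and 5%.

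**3. Small-sample caveat.** At 40 per arm and 10% in both arms, about 4 tested participants are expected per arm. The plan does not name its test statistic. Full enumeration for a Wald test from logistic regression (model-based variance, an assumption) gives a two-sided size of 1.2% for testing and 5.0% for vaccination (280 per arm, 30%). Under independence that is about 6.1% in either direction and 3.1% favouring Motivational. A pooled score test instead has size 5.9% for testing alone, slightly above nominal.

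**4. Cost of adjustment.** Holm tests the smaller p-value at 0.025 and, if it is rejected, the other at 0.05. The worst case for either outcome is having to pass at 0.025.

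| Outcome | Ratio | Power at 0.05 | Power at 0.025 | Detectable at 0.05 | Detectable at 0.025 |
|---|---|---|---|---|---|
| Testing, 28 points | 1:1 | 84.8% | 76.8% | 26.0 | 29.2 |
| Vaccination, 12 points | 1:1 | 84.3% | 76.5% | 11.3 | 12.5 |
| Testing, 28 points | 2:1 | 78.5% | 67.3% | 28.5 | 32.2 |
| Vaccination, 12 points | 2:1 | 79.5% | 70.3% | 12.1 | 13.4 |

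If both effects are real and the tests independent, Holm power for testing at 1:1 is 0.768 + (0.848 − 0.768)×0.765 = 82.9%, and for vaccination 0.765 + (0.843 − 0.765)×0.768 = 82.5%. At 2:1 the same sums give about 75% and 76%.

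**The case against.** The strongest reply is that these are two separate questions. The outcomes are numbered separately, analysed separately and powered in different samples (80 and 560), and the or in the aim may be shorthand. If each result supported only a claim about its own outcome, each would keep its own error rate and adjustment would be a matter of convention. This has force, because no section says outright that success on one outcome establishes overall efficacy. But no section says the claims are separate either, and Aim 1a and the hypothesis both join them. The reply shows that a rule is needed and does not supply one.

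Three other points stand and limit the finding:

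- The 0.05 is stated for the power calculations only. A reader might infer that the plan commits to testing each outcome at 0.05, but the analysis section gives no level. It is a reasonable inference, not a quoted commitment.
- The error figures are nominal. With so few expected testing events, the actual size depends on the statistic, as step 3 shows.
- Holm is not the only rule that would close the gap. A fixed order of testing, or an explicit statement that the two claims are separate, would also settle it. Holm is recommended because it needs no ranking of the outcomes and keeps outcome-specific claims.

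**Conclusion.** The concern holds in a limited form. The confirmatory pair has no multiplicity rule although the aim is worded so that either outcome can carry it. If each outcome is tested at two-sided 0.05, the nominal chance of at least one false-positive primary result in either direction is up to about 9.75%. The chance of a false claim favouring the Motivational arm is about 4.9%, roughly double the 2.5% for a single test. Both figures assume that both nulls are true, the tests are independent and each test has its nominal size; positive correlation lowers both.

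Two stronger readings are not supported. A reader might take 9.75% as the chance of a false efficacy claim, but it includes results in which the Motivational arm looks worse, and the hypothesis is that it does better. A reader might also set 29.2 and 12.5 points beside the plan's 28 and 12 and conclude that adjustment costs almost nothing. The former are 1:1 figures and the latter 2:1 figures, so they are not comparable. On one ratio, the worst-case loss is about 8 points of power at 1:1 (84.8% to 76.8%; 84.3% to 76.5%) and about 9 to 11 points at 2:1 (78.5% to 67.3%; 79.5% to 70.3%).

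This should be corrected before analysis.

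**What to change.** Add to the primary analysis: the two participant-level p-values, for testing and for vaccination, are tested with the Holm procedure at an overall two-sided 0.05, and efficacy on an outcome is claimed only if that outcome is rejected under Holm.

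In Power Calculations, restate the detectable differences on one allocation ratio, the 1:1 of the design. For testing (N=80) these are 26.0 points at 0.05 and 29.2 at the 0.025 first step of Holm; for vaccination (N=560), 11.3 and 12.5. Disclose that the present 28 and 12 points were computed at 2:1.

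The change needs one added rule and a restated power paragraph, with no extra participants, visits or data. The downside is power. At 28 and 12 points with 1:1 allocation, the worst case falls from about 85% and 84% to about 77% and 76%, below the planned 80%. At the 2:1 ratio now in the power section it would be about 67% and 70%.

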The scientific premise of C3 is to engage people who have been interacted with law enforcement in COVID-19 prevention (testing and/or vaccination) through social network mobilization combined with theory-driven COVID-19 prevention messaging delivered in an interactive group format. Eligible individuals will be enrolled into C3. Using a two-arm 1:1 randomized controlled trial design, 800 participants will be enrolled into either a: 1) COVID-19 prevention education arm (Education Arm) or, 2) a network mobilization change agent intervention (Motivational Arm); the latter is a Type I network intervention that includes specific training on mobilization of network members which we have adapted to COVID-19 from HIV prevention.^{2,3} Training occurs in a group-based setting of 8-10 enrolled participants facilitated by a community facilitator and Motivational Interviewing trained interventionist. At 30 days, a 15-20-minute phone booster communication session reinforces the intervention content. Information on the personal social network members of these participants will be collected during the study visit (estimated at n~2-4/participant, total~3,200) using a network elicitation and collection approach prior to randomization as in previous work.^{1,2}

Primary outcomes are: 1) the number of study participants who undergo COVID-19 testing (situation appropriate) at 3 months; and 2) the number of study participants who receive at least one COVID-19 vaccine dose at 3 months. Secondary outcomes are the same as primary, except measured among people who are in the networks of primary participants (referred to as secondary subjects moving forward). Additional secondary outcomes include: COVID-19 testing and vaccination knowledge; intent to receive a COVID-19 test or vaccination, and intent to participate in a future vaccine trial. Additional analyses will begin to understand the complex relationships between testing and vaccine statuses and proclivity to test (and potentially obtain a vaccine booster) among both study participants and their network members. For example, do those who are vaccinated serve as more effective change agents? Are vaccinated persons more or less likely to test compared to unvaccinated persons? Are people with prior COVID infection less likely to get vaccinated than those without a known history of infection? We have leveraged the RADx-UP phase I infrastructure to adapt the intervention resulting in C3.

AIMS

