
subgroups to guide future work. For the network outcomes (secondary outcome 1&2), we assume that the number of network members tested/vaccinated follows a negative binomial distribution with an over dispersion parameter equal to 2 to reflect variability among participants in terms of testing and vaccination referrals. For network testing, with a sample size of 800 participants (with an average of 2-3 named network members per participant), we would have $\geq 80\%$ power to test the null hypothesis of no difference between groups if the mean number of tested network members per participant is 0.12 in the control group and 0.25 in the intervention group (i.e., the intervention increases the proportion of participants with any network members tested from 10% to 18% and the proportion with >2 network members tested from 0.2% to 1.3%). For network vaccination, with a sample size of 560, we would have $>80\%$ power to test the null hypothesis of no difference between groups if the mean number of vaccinated network members per participant is 0.51 in the control and 0.92 in the intervention group, which reflects a scenario where the intervention increases the proportion of participants with any network members vaccinated from 30% to 41% and the proportion with more than 2 network members vaccinated from 5.1% to 12.1%. Thus, we will have sufficient power to detect effect sizes consistent with our previous work.

Attrition and missing data. All participants enrolled in the study will be included in our analyses; since the primary outcome will be measured based on testing/vaccine registry data we are confident that there will be limited missing data given that this type of registry has considerable resources to support it and is required for the EUA status. As an additional precaution, all participants will be interviewed to assess for testing/vaccination status among themselves and network members at 3 months. Thus, we anticipate very little missing outcome data. Any missing data will be addressed using multiple imputation⁷⁴ or by using a fully Bayesian approach to estimate the model⁷⁵ (in which missing data are essentially treated as additional unknown parameters).

POTENTIAL RISKS AND BENEFITS TO SUBJECTS

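### The network-testing power figure rests on a control mean of 0.12 tested members per participant, 3 to 6 times what the plan's own eligibility and testing rates imply, with no derivation given

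*Combined protocol and SAP*

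**What the plan says.** Power Calculations sets the testing inputs first. Eligibility is fixed by "assuming that of the 800 total participants and their network members, 10% would meet the current CDC recommended criteria for testing", so network members are expressly covered. Uptake follows: "We estimated 3-month testing rates among those eligible for testing of 10% in the control group". For participant testing, the eligibility share cuts the sample from 800 to 80.

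The network-testing paragraph then uses all 800 participants, an average of 2-3 named members each, and a negative binomial count with overdispersion 2. It claims at least 80% power "if the mean number of tested network members per participant is 0.12 in the control group and 0.25 in the intervention group", and translates the means into 10% versus 18% of participants with any member tested. It ends without qualification: "Thus, we will have sufficient power to detect effect sizes consistent with our previous work".

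On the outcome itself, Study Design says "Secondary outcomes are the same as primary, except measured among people who are in the networks of primary participants", and Aim 1a applies the situation-appropriate testing endpoint to secondary subjects as well as participants. Allocation differs between sections. The power work used "alpha=0.05, two-sided tests, and a 2:1 ratio of randomization to the intervention vs. control group", while Randomization states: "Study participants will be randomized to receive the Education or Motivational intervention at a 1:1 ratio".

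**The concern.** The two eligibility and uptake rates, multiplied by the number of members, fix a control mean for situation-appropriate tests. The value used is several times larger and no source is given for it. Network testing is also the only one of the four main outcome calculations that keeps the full 800; participant testing uses 80, and both vaccination outcomes use 560.

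Diffusion through networks is the premise of the trial, and network testing is a named secondary outcome under Aim 1a. If the sufficient-power sentence stands and the network-testing comparison is null, a reader could take that as evidence against diffusion when the study may have had little chance of detecting a doubling.

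**Working it through.** **Inputs.** From Power Calculations: N = 800; dispersion 2; means 0.12 and 0.25; two-sided alpha 0.05; 10% eligible; 10% tested among eligible controls; 2-3 members. From Study Design: 2-4 members, about 3,200 in total, i.e. 3,200/800 = 4 per participant. Allocation is 1:1 in the design and 2:1 in the power section.

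**Formula.** Wald test of the log rate ratio: var = (1/m0 + 2)/n0 + (1/m1 + 2)/n1; power = Φ(ln(m1/m0)/√var − 1.96).

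**Step 1: the plan's own figure.** ln(0.25/0.12) = ln 2.083 = 0.734.
- 1:1 (400/400): var = 10.333/400 + 6/400 = 0.0408; 0.734/0.202 = 3.63; power 95%.
- 2:1 (267 control/533 intervention): var = 0.03875 + 0.01125 = 0.0500; 0.734/0.2236 = 3.28; power 91%.

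The companion proportions also reproduce. The share with any member tested is 1 − (1 + 2m)^(−1/2), which is 10.2% at 0.12 and 18.4% at 0.25.

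**Step 2: control mean implied by the stated rates.** Members × 0.10 × 0.10 gives 0.02 (2 members), 0.03 (3) and 0.04 (4). The ratios are 0.12/0.02 = 6, 0.12/0.03 = 4 and 0.12/0.04 = 3. Among 400 controls, 2-3 members imply 8 to 12 tested members, against 400 × 0.12 = 48 assumed. Reaching 0.12 with 10% eligible and 2-3 members would need 40-60% of eligible control members to test.

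**Step 3: power at the implied means, rate ratio held at 2.083.**

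| Members | m0 | m1 | Power 1:1 | Power 2:1 |
|---|---|---|---|---|
| 2 | 0.02 | 0.0417 | 38% | 32% |
| 2.5 | 0.025 | 0.0521 | 46% | 38% |
| 3 | 0.03 | 0.0625 | 52% | 44% |
| 4 | 0.04 | 0.0833 | 63% | 54% |

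First row at 1:1: var = 52/400 + 26/400 = 0.195; 0.734/0.4416 = 1.66; Φ(−0.30) = 38%. Simulation with a fitted negative binomial model (1,500 runs per scenario, 2 and 3 members) gave 34% and 54% at 1:1, and 27% and 41% at 2:1.

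**Step 4: detectable effect.** For 80% power with 2-3 members, the rate ratio must be about 2.7-3.2 at 1:1 or 3.0-3.8 at 2:1.

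**The case against.** **The network outcome may mean any test.** Primary Outcomes states the eligibility restriction for participants in the primary testing analysis. Secondary Outcome then defines at least one test in a network member with no such condition. The analysis section counts all tested members and offsets by full network size. Situational information is described for the participant's own assessment, not for contacts. On this reading 0.02-0.03 is only a floor. Eligible members contribute 0.10 × 0.10 = 1% per member, and 0.12 requires 6% per member with 2 members or 4% with 3. The ineligible 90% would then have to test at (0.06 − 0.01)/0.9 = 5.6% or (0.04 − 0.01)/0.9 = 3.3%. The documents give no rate for such testing. The ambiguity stands, because Study Design and Aim 1a point the other way. It leaves 0.12 without a source; it does not justify it.

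**The control rates alone do not fix power.** This also stands. The 2.08 ratio is stated only for the 0.12 baseline. Taking instead the 38% versus 10% from the participant testing calculation, the means become 0.076-0.114 against 0.02-0.03, and power is 90-98% at 1:1 or 81-93% at 2:1. But 38% is the minimum detectable rate for 80 participants, a 3.8-fold effect, not an expected one. Relying on it would mean that network testing is powered for a near-quadrupling, which the plan does not say.

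**The section is hedged.** It calls its estimates conservative and says power rises with broader eligibility, higher prevalence or member-level analysis. That is fair context, but the closing sentence carries no such condition.

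**Conclusion.** The point holds as a conflict between inputs. The control mean of 0.12 is 4 to 6 times the value implied by the same section's rates at 2-3 members, and 3 times at 4 members. If only eligible members' tests count and the 2.08 ratio is kept, power at 2-3 members is about 38-52% (1:1) or 32-44% (2:1). At 4 members it is 63% or 54%. None of these reaches 80%, so on those assumptions the sufficient-power conclusion is wrong as written for network testing.

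A reader might infer three stronger things that the documents do not support:
- **That the 80% claim is an arithmetic error.** It is conditional on its means and true for them.
- **That the plan's rates by themselves give 38-52% power.** That range also needs the carried-over ratio, 1:1 allocation, 2-3 members and the restricted outcome.
- **That the eligibility step was demonstrably forgotten.** The 10% with any member tested does match the 10% rate among eligible people, which is suggestive, but the text does not show how 0.12 was reached.

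**What to change.** State whether the network-testing outcome is restricted to situation-appropriate tests, and make Study Design, Aim 1a, Secondary Outcome and the outcome analysis section agree.

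- **If restricted:** restate the network-testing power, or the detectable rate ratio, from the 10% eligibility and 10% uptake inputs at 1:1, naming the network size and rate ratio assumed. Remove network testing from the sufficient-power sentence. With 2-3 members the figures are about 38-52% power at a ratio of 2.08, or a detectable ratio of about 2.7-3.2.
- **If any test counts:** say so wherever the outcome is defined, and give the any-test rate among network members, with its source, that supports 0.12.

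The change is to wording only; sample size and conduct are unaffected. Its cost is that the stated power for a secondary outcome becomes less favourable under the restricted definition.
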